4. GENERAL CONSIDERATIONS

4.1. Tables, Figures, and Listings

Summaries will be presented by treatment (placebo, ataluren) and in total (where applicable). Summary statistics for continuous variables will include n (number of subjects), mean, standard deviation, median, minimum, and maximum. Summary statistics for categorical variables will include N (number of subjects in population), n (number of subjects in category), and % (percent of subjects in category). Where applicable, the summary data (eg, mean, standard error) will also be provided in graphical presentation. Unless otherwise specified, all inferential analyses will be 2-sided at the alpha (α) of 0.05 level of significance.

By-subject data listings will be created for each eCRF domain sorted by treatment, subject, and associated dates, where applicable.

4.2. Baseline and Endpoint Definitions

Baseline is defined as the last available measurement prior to the first dose of double-blind study drug unless specified otherwise.

Baseline 6MWD is defined as the maximum measurement of valid Day 1 and Day 2 6MWD values.

Similarly, the Week 72 6MWD will be defined as the maximum of the 6MWDs from a valid 6MWT on Day 1 and Day 2 at Week 72 visit.

4.3. Baseline Characteristics and Treatment Group Comparability

Baseline subject characteristics for each study population, will be summarized using frequency tables for categorical variables and descriptive statistics for quantitative variables. The baseline measurements will be included in the analysis model as a covariate for the primary and secondary efficacy endpoints. Details are specified in Section 6.

4.4. Interim Analyses

There are no planned interim analyses.

4.5. Multicenter Study

Summary statistics will be provided by geographic region (North and Latin America, Europe, and Asia Pacific) and/or country and displayed graphically to examine potential region effects for the primary endpoint as needed. No statistical tests in this regard will be conducted.

4.6. Multiplicity Control

In order to control the family-wise error rate for the primary and key secondary efficacy endpoints, a fixed sequence procedure will be used. Testing orders of the primary endpoint and the key secondary endpoints are listed in the table below.

Table 1: Test Sequences

| |
|--|
| Primary Endpoint |
| Slope of change in 6-minute walk distance (6MWD) over 72 weeks (mITT) |
| Key Secondary Endpoints |
| (1) Slope of composite of average change in times to run/walk 10 meters, climb 4 stairs, and descend 4 stairs over 72 weeks (mITT) |
| (2) Change from baseline to Week 72 in North Star Ambulatory (NSAA) total score (mITT) |

Abbreviations: 6MWD, 6-minute walk distance; mITT, modified intention-to-treat; NSAA, North Star Ambulatory Assessment

The primary endpoint will be tested at the significance level of 0.05 (two-sided). If $p < 0.05$, then the primary endpoint will be considered statistically significant, and the study will be declared positive. If the test of the primary endpoint is statistically significant, then the key secondary endpoints will be tested in the order specified in the table above, each at the 0.05 (two-sided) significance level. Only if the first key secondary endpoint is statistically significant at the 0.05 significance level, the second key secondary endpoint will be tested also at the 0.05 significance level.

4.7. Missing Data Handling

The 12-week interval of patient visits permits inclusion of 6 post-baseline evaluations of efficacy during the randomized study period (Weeks 12, 24, 36, 48, 60, and 72), ensuring that time trends can be adequately assessed, and that sporadically missing data do not have a substantial impact on data analysis.

The analyses using a mixed model repeated measures (MMRM) model will be performed based on available data assuming the missing assessments are missing at random (MAR). As sensitivity analyses, missing assessments for the primary and key secondary endpoints based on the analysis of covariance (ANCOVA) will be imputed using pattern-mixture multiple imputation (MI) as described in Section 6. Detailed imputation method is described in [Appendix 2](#).

Missing data will not be imputed for summaries for all safety endpoints and for by-visit summaries for efficacy endpoints.

4.8. Study Analysis Visit

Study analysis visits during double-blind treatment period will be derived as listed in [Table 2](#) based on days from randomization date to the corresponding visit date. Study analysis visits will be used in all by-visit summaries for both efficacy and safety assessments.

Table 2: Study Analysis Visit

| Analysis Visit | Scheduled Visit Number (Study Day) | Analysis Window (Study Day) |
|----------------|------------------------------------|---|
| DB Week 12 | Visit 3 (85) | [43, 126] |
| DB Week 24 | Visit 4 (169) | [127, 210] |
| DB Week 36 | Visit 5 (253) | [211, 294] |
| DB Week 48 | Visit 6 (337) | [295, 378] |
| DB Week 60 | Visit 7 (421) | [379, 462] |
| DB Week 72 | Visit 8 (505) | Any double-blind visit occurred on or after Day 463 |

Abbreviations: DB, double-blind.

Study day is calculated as visit date - randomization date + 1.

All assessments will be assigned to a study analysis visit based on study days. For a given subject, if multiple assessments are within the same analysis window, the one closest to the scheduled study day will be used for that analysis visit. In case of equal number of days to the scheduled visit date, the later assessment will be used for that given analysis visit.

For 6MWD at the Week 72 Visit (Visit 8), the date corresponding to the maximum of Day 1 and Day 2 will be used for deriving the study analysis visit.

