4.10. Addressing the Impact of Coronavirus Disease of 2019 (COVID19)

Study visits have been impacted by site closures and travel restrictions due to Coronavirus Disease of 2019 (COVID19). Mitigation strategies have been implemented to reduce the number of missed or delayed visits for the study, including allowing subjects to have visits outside of the protocol defined window (± 7 days). To minimize the impact from the out-of-window assessments, the actual week, instead of nominal visit, will be used in statistical modelling, where appropriate.

The protocol described MMRM model using actual week at the visit will be considered as primary efficacy analysis method. The protocol proposed the analysis of ANCOVA model analyzing 6MWD at Week 72 after MI assumes that almost all subjects have visits within protocol defined window will be considered as sensitivity analysis.

In addition, to assess the impact of COVID19, a sensitivity analysis for 6MWD using MMRM and ANCOVA after MI after removing all COVID19 impacted visits will be performed for mITT and ITT populations as described in Section [6.1.3.6](#).

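### The closest-to-Day-505 rule in double-blind SAP 4.8 can let a late Visit 7 replace a completed Visit 8 as the Week 72 value, contrary to the Week 72 definition in 4.2

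*SAP*

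**What the plan says.** Double-blind SAP 4.8 bases the analysis visit on timing alone: "All assessments will be assigned to a study analysis visit based on study days". In its Table 2, Week 60 has target Day 421 and window Days 379 to 462. Week 72 has target Day 505 and takes "Any double-blind visit occurred on or after Day 463". If several assessments share a window, "the one closest to the scheduled study day will be used for that analysis visit". On ties, "In case of equal number of days to the scheduled visit date, the later assessment will be used". The only sentence in 4.8 specific to Visit 8 says which of its two walk dates is used for windowing. It gives Visit 8 no precedence.

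Section 4.2 defines the endpoint by visit: "the Week 72 6MWD will be defined as the maximum of the 6MWDs from a valid 6MWT on Day 1 and Day 2 at Week" (meaning the Week 72 visit). Under 2.7.1, two walks are scheduled at Visit 8 and no second walk is named for Visit 7.

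Section 4.10 reports site closures and travel restrictions, and mitigation "including allowing subjects to have visits outside of the protocol defined window" of ±7 days. It gives no number or length of delays.

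The open-label SAP (4.9, Table 1) uses the same closest-day rule but ends the Week 72 window at Day 546.

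**The concern.** Two definitions of Week 72 sit side by side, one by study day (4.8) and one by visit (4.2), and the SAP does not say which governs when they disagree. They disagree when both late visits land in the Week 72 window and Visit 7 is nearer Day 505. The value analysed as Week 72 is then the Week 60 assessment, and the completed end-of-treatment assessment is left out. For 6MWD, a best-of-two baseline is compared with a single later walk.

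The windows determine the 6MWD ANCOVA after MI (6.1.3.1), the by-visit tables and, in effect, the Week 72 rNSAA ANCOVA after MI (6.2.1.2), which is the second key secondary analysis. They also determine the categorical-visit MMRM that section 3.1.1 of the document on changes from the planned analysis makes primary. That model gives up the use of actual week, which 4.10 had adopted to deal with out-of-window visits.

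**Working it through.** **Inputs.** Targets and windows: double-blind SAP 4.8, Table 2, and open-label SAP 4.9, Table 1. Hypothesised difference of 1.0 m/week: double-blind SAP 2.4. The within-boy SD of a single walk and the share of boys affected are not in the documents; the values below are assumptions.

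**1. The plan's own figures.** Target day = 7 × week + 1, so Week 60 = 421 and Week 72 = 505. Midpoint = (421 + 505)/2 = 463. Both targets and the Day 463 boundary match Table 2.

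**2. When the swap occurs.** Let d7 and d8 be the study days of Visits 7 and 8, with d7 < d8.
- Visit 7 enters the Week 72 window if d7 ≥ 463, that is 463 − 421 = 42 days late or more.
- For d7 ≤ 505 < d8, Visit 7 is closer if 505 − d7 < d8 − 505, that is d7 + d8 > 1010.
- If the sum is exactly 1010, the tie rule keeps Visit 8.

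**3. Cases.**

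| Visit 7 | Visit 8 | Distances from Day 505 | Double-blind Week 72 | Open-label Week 72 (cap Day 546) |
|---|---|---|---|---|
| 470 | 512 | 35, 7 | Visit 8 | Visit 8 |
| 480 | 530 | 25, 25 | Visit 8 (tie) | Visit 8 (tie) |
| 480 | 540 | 25, 35 | Visit 7 | Visit 7 |
| 463 | 547 | 42, 42 | Visit 8 (tie) | Visit 7 (Visit 8 is past the cap) |
| 463 | 548 | 42, 43 | Visit 7 | Visit 7 (Visit 8 is past the cap) |

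Week 60 has no value in any of these rows.

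If both visits slip by D days, the condition is 926 + 2D > 1010, so the swap starts at D = 43. If Visit 8 is no more than 7 days late (Day 512), Visit 7 must fall on Day 499 or later, 78 days late.

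**4. Size for one affected boy (6MWD).** The expected maximum of two independent normal walks exceeds one walk by SD/√π = 0.564 SD. For an assumed SD of 10, 20 or 30 m this is 5.6, 11.3 or 16.9 m.

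In the 480/540 case the value used is (540 − 480)/7 = 8.6 weeks earlier, which raises it if the boy is declining. The two effects cancel at a decline of 5.6/8.6 ≈ 0.7 m/week (SD 10 m) to 16.9/8.6 ≈ 2.0 m/week (SD 30 m).

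**5. Size for the treatment difference.** At 1.0 m/week the expected difference is (480 − 1)/7 = 68.4 m on Day 480 and (540 − 1)/7 = 77.0 m on Day 540, against 72 m nominal. If 2%, 5% or 10% of boys were affected in this way, the Week 72 difference would fall by 0.02, 0.05 or 0.10 × 8.57, about 0.2, 0.4 or 0.9 m, relative to using Visit 8.

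**The case against.** Closest-to-target windowing is a legitimate choice, and Day 480 is nearer to Week 72 than Day 540. Section 4.2 can be read as the specific rule that protects Visit 8 for 6MWD, since 4.8 itself calls Visit 8 the Week 72 visit and 3.4 speaks of a valid Visit 8 walk within the Week 72 window. On that reading only a precedence sentence is missing. That is a fair description of the gap, but the sentence is needed: a programmer following 4.8 would drop Visit 8, and 4.2 offers no protection for rNSAA.

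It can also be said that late visits were anticipated. The planned primary model uses actual weeks and all valid assessments (section 6), so it keeps both visits. Section 4.10 makes the 6MWD ANCOVA a sensitivity analysis because it assumes nearly all visits were in window. Section 6.1.3.6 repeats the 6MWD analyses without COVID-affected visits. This stands in part. That analysis removes visits rather than relabelling them, and it covers only 6MWD. The empty Week 60 matters little for the ANCOVA, because only Week 72 is analysed and the affected boy has an observed value there.

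A reader might infer more than the documents support:
- **That the missing upper limit is the cause.** It is not: the 480/540 swap also occurs under the open-label cap of Day 546.
- **That a late Visit 7 is enough.** Both timing conditions are needed.
- **That the result is biased towards one arm.** Visits were scheduled under blinding, and nothing ties the delays to treatment.
- **That 6MWD is understated in affected boys.** The protocol (11.2.3) expects decline after age 7, so the earlier date works the other way.
- **That Week 144 needs the same rule.** Visit 10 would have to be 925 − 841 = 84 days late, only one walk is scheduled at Visit 11, and Visit 11 is also the premature-discontinuation visit.

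**Conclusion.** The point holds as a minor specification gap. As written, 4.8 discards a completed Visit 8 in favour of Visit 7 when Visit 7 falls on Day 463 or later and the two study days sum to more than 1010, and this is inconsistent with 4.2. The two SAPs can also give the same boy different Week 72 values (Days 463 and 547).

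How often this occurred cannot be found from the documents; they do not show that it happened at all. The effect should be similar in both arms and small: about 0.2 to 0.9 m on the Week 72 difference, if 2% to 10% of boys were affected as in the 480/540 example and the hypothesised 1.0 m/week applied. For an affected boy, the 6 to 17 m loss rests on an assumed SD of 10 to 30 m and is partly offset by the earlier date, so the net sign is unknown. The two-walk loss does not apply to rNSAA, which has no such maximum. The planned slope analysis, the sample size and the significance level are untouched.

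**What to change.** In double-blind SAP 4.8, and for Week 72 in open-label SAP 4.9, add: when Visit 7 and a completed Visit 8 both fall in the Week 72 window, Visit 8 is the Week 72 value, consistent with 4.2, and Visit 7 is used for Week 60 if that window is otherwise empty. If Visit 8 was not done, the current day-based rule stays, so that a real value close to Day 505 is not moved away and Week 72 left to imputation.

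The two SAPs should also be reconciled for a Visit 8 after Day 546, because there Visit 8 leaves the open-label Week 72 window and the added sentence does not apply.

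Do not extend the rule by visit number to Visit 11: an early-termination assessment could then be labelled Week 144.

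Report the number of boys, by arm, with Visit 7 on Day 463 or later and study days summing to more than 1010, and separately any whose Week 72 value differs between the two SAPs. If there are any, re-derive and report the affected analyses. The open-label SAP dates the first database lock at 11 April 2022, so the double-blind change should be documented as made after that lock.

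The cost is one sentence and a small derivation change. The downside is that some values labelled Week 60 or Week 72 will lie further from their target day.

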4.9. Merging Strata

If one of the strata includes subjects from only one of the two treatment arms in ITT, mITT, and PP populations, the stratum cell will be combined with the closest neighbor stratum cell based on the patients' baseline assessments within corresponding stratum for the corresponding population.

4.10. Addressing the Impact of Coronavirus Disease of 2019 (COVID19)

Study visits have been impacted by site closures and travel restrictions due to Coronavirus Disease of 2019 (COVID19). Mitigation strategies have been implemented to reduce the number of missed or delayed visits for the study, including allowing subjects to have visits outside of the protocol defined window (± 7 days). To minimize the impact from the out-of-window assessments, the actual week, instead of nominal visit, will be used in statistical modelling, where appropriate.

The protocol described MMRM model using actual week at the visit will be considered as primary efficacy analysis method. The protocol proposed the analysis of ANCOVA model analyzing 6MWD at Week 72 after MI assumes that almost all subjects have visits within protocol defined window will be considered as sensitivity analysis.

In addition, to assess the impact of COVID19, a sensitivity analysis for 6MWD using MMRM and ANCOVA after MI after removing all COVID19 impacted visits will be performed for mITT and ITT populations as described in Section [6.1.3.6](#).

5. SUBJECT DATA

5.1. Subject Disposition and Study Populations

The number of subjects screened, randomized, discontinued early during the double-blind treatment period (along with reasons for discontinuation) will be summarized. The number of subjects randomized will also be summarized by region, country, and site.

The number of subjects in the ITT, mITT, as-treated, and PP populations (along with reasons excluded from the ITT and PP populations) will be summarized.

The number of subjects with major protocol deviation will also be summarized for ITT, mITT, and as-treated populations.

5.2. Duration of Treatment with Study Drug

Duration of treatment with study drug will be calculated as:

$$\begin{aligned} \text{Duration (days)} \\ &= \text{Date of last dose of double-blind study drug} \\ &\quad - \text{Date of first dose of study drug} + 1 \end{aligned}$$

Duration of treatment with study drug in weeks will be summarized continuously and categorically (<12 weeks, 12 to <24 weeks, 24 to <36 weeks, 36 to <48 weeks, 48 to <60 weeks, 60 to <72 weeks, ≥72 weeks) based on ITT, mITT, and as-treated populations.

5.3. Study Drug Compliance

To evaluate study drug compliance, number of subjects with treatment interruption, and the duration of treatment interruptions will be summarized for ITT, mITT, and as-treated populations.

5.4. Demographic and Baseline Characteristics

Demographic and baseline characteristics including age, gender, race, ethnicity, region (North and Latin America, Europe, and Asia Pacific), country, height, weight, body mass index (BMI), steroid use at baseline, baseline 6MWD, and baseline time to stand from supine will be summarized for ITT, mITT, PP, and as-treated populations.

5.5. Disease Characteristics

Disease characteristics including age at onset of phenotypic evidence of dystrophinopathy, age at first observation of difficulty with ambulation, age at diagnosis of dystrophinopathy, signs/symptoms/laboratory results used to support diagnosis, prior dystrophin gene sequencing, location of nonsense point mutation, and stop codon type will be summarized for ITT, mITT, and PP populations.

5.6. Medical History

Medical history of dystrophinopathy will be summarized with disease characteristics as described in Section 5.5. Medical history other than dystrophinopathy will be presented in the by-subject listing for as-treated population.

5.7. Concomitant Medications and Non-Drug Treatments

Concomitant medications and non-drug treatments will be coded using the World Health Organization Drug Dictionary (WHODD), version September 2021 or higher.

Prior medications and non-drug treatments are defined as those taken any time prior to Day 1. Concomitant medications and non-drug treatments for double-blind period are defined as those taken any time during the double-blind treatment period (Day 1 to the date prior to the first dose of open-label study treatment, inclusive).

The use of prior and concomitant medications and non-drug treatments will be summarized by Anatomical Therapeutic Chemical (ATC) Level 3 and preferred term (PT) for ITT, mITT, and as-treated populations. In addition, corticosteroids use at baseline and the incidence of changes in regimen of corticosteroids will be summarized for ITT, mITT, and as-treated populations.

6. EFFICACY EVALUATION

Unless otherwise specified, the actual weeks at each visit will be used for all MMRM analyses using all valid assessments. The by-visit summaries will be generated based on the analysis visits described in Section 4.8.

6.1. Primary Efficacy Variable (6MWD)

6.1.1. By-Visit Summary

The mean and mean changes from baseline in 6MWD will be summarized by treatment group at each visit. For these summaries, any subjects who lose ambulation during the study will be assigned a 6MWT result of 0 meters for the visit in which the subjects lose ambulation and for all remaining visits while they participate in the study.

6.1.2. Primary Analysis

The rate of change in 6MWD over 72 weeks (slope) in the mITT population will be considered as the primary efficacy endpoint.

A MMRM model will be employed using a random intercept and a random slope of change per week using observed data assuming the missing assessments are MAR. The slope will be compared between ataluren and placebo, and the estimated treatment difference with corresponding 95% confidence interval (CI) will be provided. The estimated difference in the change at Week 72 will also be provided to facilitate interpretation. The MMRM model will include baseline concomitant corticosteroid type (deflazacort, prednisone/prednisolone), baseline 6MWD category (<300 meters, 300 to <350 meters, 350 to <400 meters, ≥400 meters), baseline 6MWD, treatment, week (actual week at the visit as a continuous variable), the interaction of week and baseline 6MWD, and the interaction of week and treatment. The unstructured covariance matrix (UN) will be used in the MMRM model. Other types of covariance matrix (heterogenous Toeplitz, Toeplitz, and compound symmetric) will be explored in the case of non-convergence of UN. For this analysis, any subjects who lose ambulation during the study will be assigned a 6MWT result of 0 meters for the first visit in which the subjects lose ambulation and set for missing for all visits afterwards while they participate in the study.

The primary endpoint will be tested at the significance level of 0.05 (two-sided). If $p < 0.05$, then the primary endpoint will be considered statistically significant, and the study will be declared positive.

The example SAS code is listed below:

```
PROC MIXED data=<dataset> method=reml;  
  CLASS Cortico Subjid Trt C6WMD;  
  MODEL N6WMD = Cortico C6WMD Trt B6WMD Week Week*B6WMD  
    Week*TRT/S CL;  
  RANDOM Int Week/type=un subject=Subjid;  
  LSMEANS TRT / pdiff at Week=72 CL;  
RUN;
```

where

N6WMD = 6WMD at each visit (Baseline to Week 72)

B6WMD = Baseline 6WMD
C6WMD = Baseline 6WMD category
Cortico = Baseline concomitant corticosteroid type
Week = Actual study week at each visit
Trt = Treatment group
Subjid = Subject
Int = Intercept

6.1.3. Supportive/Sensitivity Analyses

6.1.3.1. Analysis of Covariance (ANCOVA) Using Multiple Imputation (MI)

As a sensitivity analysis, an ANCOVA model will be used to evaluate the difference in change in 6MWD from baseline to Week 72 after missing data have been imputed via a pattern mixture model utilizing MI. The estimated treatment difference in change from baseline of 6MWD at Week 72 and the corresponding 95% confidence interval (CI) will be provided. The ANCOVA model will include baseline concomitant corticosteroid type (deflazacort, prednisone/prednisolone), baseline 6WMD category (<300 meters, 300 to <350 meters, 350 to <400 meters, ≥ 400 meters), treatment, as well as baseline 6MWD as a covariate. For this analysis, all 6MWD will be assigned to an analysis visit according to the analysis visit window described in Section 4.8. Any subjects who lose ambulation during the study will be assigned a 6MWT result of 0 meters for the visit in which the subjects lose ambulation and for all remaining visits while they participate in the study. For subjects with missing 6MWD due to other reasons, the missing assessments at post-baseline visits will be imputed using the pattern-mixture model MI assuming the missing values are missing not at random (MNAR) utilizing the complete case missing value pattern (CCMV - subjects who completed primary efficacy assessments without missing values). Detailed imputation method is described in [Appendix 2](#).

The example SAS code is listed below:

```
PROC MIXED data=<dataset> method=reml;  
  CLASS Cortico Trt C6MWD;  
  MODEL CHG6MWD = Cortico C6MWD Trt B6MWD /CL;  
  LSMEANS TRT / pdiff CL;  
RUN;
```

where

CHG6MWD = change from baseline in 6MWD at Week 72
B6MWD = Baseline 6MWD
C6MWD = Baseline 6MWD category
Cortico = Baseline concomitant corticosteroid type
Trt = Treatment group

